#### 4.2.1.4 Final Population PK Model

At the end of covariate testing, alternative variance-covariance structures for  $\Omega$  will be evaluated including partial and full block structures. Such a structure is deemed suitable if it provides a statistically significant ( $p < 0.001$ ) improvement in the model OFV and if it improves model stability as measured by the condition number and/or a successful covariance step. The model that results from this step of the model building process is considered the final model.

Further criteria for accepting a model as the final run includes the following:

- The minimization (for gradient methods) is successful.
- There are no estimates close to a boundary.
- Relative standard errors (RSE) of the estimates should be  $< 30\%$  for fixed-effect parameters and  $< 50\%$  for random-effect parameters.
- There are no unacceptable trends in goodness-of-fit plots.
- The model allows for the goal of the analysis to be met.
- The parameter shrinkage is acceptable.
- Population PK parameter estimates from the final model will be presented, including bodyweight-adjusted clearance for each bodyweight category (adjusted to the mean bodyweight of each weight category). Additionally, the post-hoc individual PK parameter estimates (including AUC0-inf) will be summarized.

#### 4.2.1.5 Evaluation of the Final Population PK Model

Model qualification will be based on criteria including successful numerical convergence, acceptable goodness of fit plots with no indication of bias, adequate precision in parameter estimates evaluating shrinkage in important parameters (CL, V and Ka parameters). In addition, Visual Predictive Checks (VPCs) will be used to evaluate the predictive ability of the final model. Where applicable, VPCs will be performed with prediction correction. Plots of observed data distributions will be compared with simulated distributions to demonstrate the model's ability to adequately predict the data on which the model was based. VPCs will be based on at least 500 simulations and will be stratified by covariates of

potential interest. Specifically, VPCs will be stratified by cohort, route of administration and weight category.

#### 4.2.1.6 Handling of Missing Data and LLOQ

Individual concentrations below the Lower Limit of Quantification (LLOQ) of the bioanalytical assay will be reported as NQ (Not Quantifiable) in the listings with the LLOQ defined in the footnotes of the relevant tables, listings and figures. Individual serum concentrations that are Not Reportable will be reported as NR and those that are missing will be reported as NS (No Sample) in the listings. Serum concentrations that are NQ, NR or NS will be handled as follows for the provision of descriptive statistics:

- Any values reported as NR or NS will be excluded from the summary tables and corresponding figures.
- At a time point where less than or equal to 50% of the concentration values are NQ, all NQ values will be set to the LLOQ, and all descriptive statistics will be calculated accordingly.
- At a time point where more than 50% (but not all) of the values are NQ, the gmean, gmean  $\pm$  gSD and geometric coefficient of variation (gCV) will be set to NC. The maximum value will be reported from the individual data, and the minimum and median will be set to NQ.
- If all concentrations are NQ at a time point, no descriptive statistics will be calculated for that time point. The gmean, minimum, median and maximum will be reported as NQ and the gCV and gmean  $\pm$  gSD as NC.
- The number of values below LLOQ ( $n < LLOQ$ ) will be reported for each time point together with the total number of collected values ( $n$ ).

Three observations  $>$  LLOQ are required as a minimum for a serum concentration or PK parameter (eg, Cmax, Clast) to be summarized. Two observations  $>$  LLOQ are presented as minimum and maximum with the other summary statistics as NC.

For AZD7442 concentration derived as the sum of AZD1061 and AZD8895 concentrations, the following cases of  $<$  LLOQ or missing hold:

AZD1061 concentration	AZD8895 concentration	Result of AZD7442 concentration
< LLOQ	< LLOQ	< LLOQ
< LLOQ	XX	XX
YY	< LLOQ	YY
YY	XX	YY + XX
Missing	XX	Missing
YY	Missing	Missing
Missing	Missing	Missing

#### 4.2.1.7 Population PK Analysis

Pharmacokinetic data from all cohorts, routes of administration and age group/weight categories will be analysed simultaneously by population PK approaches.

##### 4.2.1.7.1 Dataset to Develop the Population PK Model

A population model based on adult studies are under development. The AZD7442 population PK structural model will be developed based on serum concentration time- profile from the Phase I study (D8850C00001) conducted in healthy adult subjects, Phase III studies conducted in adult patients that will include at least studies D8850C00002,

D8850C00003, D8851C00001 and ACTIV-3 and paediatric PK/PD/safety study D8850C00006, when data are available. Individuals will be defined as evaluable for the population PK analysis if they have at least one AZD7442 post-dose serum sample that are above the lower limit of quantification (LLOQ). Missing data will not be imputed.

Concentrations below the LLOQ will be handled with the M3 method. Population PK data from this study as defined in section 4.2.1.7 will be added to the adult population PK dataset. A brief description of the minimum studies to be included in the dataset is provided in [Table 5 Description of the studies to be included in the population PK analysis](#), in the appendix.

##### 4.2.1.7.2 Data analysis methods

The analysis will be carried out according to the FDA and EMA guidances “Guidance for Industry: Population Pharmacokinetics” and “Guidance on Reporting the Results of Population Pharmacokinetic Analyses”, respectively.

##### 4.2.1.7.3 Covariates to be used in the analysis

This updated Population PK model will account for clinically relevant covariates and will include a weight-based allometric scaling of clearance and volume, with fix allometric exponents along with an age-based maturation function for clearance. Covariates in the

latest adult population PK model will be included such as age, body weight, sex, race and eGFR co-morbidity etc. Additional covariates such as body surface area (BSA), body mass index (BMI), albumin, anti-drug antibodies, hepatic function, renal function, SARS-CoV-2 infected or not, viral load, severity of disease, asymptomatic or not, and different co-morbidities may be evaluated as well if deemed appropriate. Co-linearity among covariates will be examined. For pairs with correlation > 80%, a determination will be made as to which variable to retain based on factors such as clinical relevance consistency of variable. The covariates, whenever available, for the population PK analysis will be collected for all subjects who have received AZD7442 and had at least 1 valid serum concentrations. The assessment of each categorical covariate will be done if enough data are available to perform the test, ie if more than 20 subjects or more than 10% of subjects represent this subgroup of covariate. Race will be tested and potentially combined if deemed appropriate, such as combining all Asian populations.

### **Demographics and baseline clinical chemistry covariates in consideration for investigation**

- Route of Administration (1 = IV Intra Venous; 2 = IM Intra Muscularly)
- Sex (SEX), 1 = males and 0 = females
- Race (RACE), 1 = White; 2 = Black; 3 = Asian; 4 = Other
- Age (AGE), year, weeks
- Body weight (WT), kg
- BMI (kg/m^2)
- Alanine Aminotransferase (ALT)
- Aspartate aminotransferase (AST)
- Estimated Glomerular Filtration Rate (eGFR)
- Serum Creatinine (SCR)
- Total Bilirubin (BIL)
- Serum Albumin
- Co-morbidity information
- Viral Load

Covariates that change over time will be considered in order to obtain values that match the observation time of the dependent variable, such as age and body weight especially in the paediatric patients.

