1.3 Schedule of Activities

Table 1 summarizes the SoA at screening for all participants. **Table 2** and **Table 3** summarize the SoA during the main study for neonates (modified sample collection) and non-neonates, respectively.

Table 1 Schedule of Activities: Screening Period (All Participants)

Procedure/study day	Day -7 to Day 1 ^a	For details, see section:
Informed consent/assent	X	5.1
Assignment SID number ^b	X	6.3
Demographics and risk categorization	X	5.1
Medical history	X	NA
Complete physical examination, including height and weight	X	8.2.1
Vital signs (including pulse oximetry)	X	8.2.2
Triple 12-lead ECG	X	8.2.3
Serum chemistry, hematology, urinalysis ^c	X	8.2.4

Table 1 Schedule of Activities: Screening Period (All Participants)

Procedure/study day	Day -7 to Day 1 ^a		For details, see section:
Coagulation	X		8.2.4
Urine pregnancy test (post-pubertal females only) ^d	X		8.2.4.5
Assessment of SAEs	X		8.3
Concomitant medications	X		6.5
Serum sample for SARS-CoV-2 serology (anti-nucleocapsid) testing (all participants other than neonates)	X		8.5.3.2
Verify eligibility criteria	X		5.1, 5.2
Screening criteria specific to each cohort	Cohort 1 Pre-exposure prophylaxis	Cohorts 2 and 3 Treatment of COVID-19	For details, see section:
Documented SARS-CoV-2 RT-PCR test taken \leq 3 days before Day 1 ^c OR Rapid SARS-CoV-2 antigen test (for assignment to study cohorts) per local standard of care authorized for screening or diagnosis	X (negative)	X (positive)	8.6.1
COVID-19 Symptom screen	NA	X (Yes)	5.1

^a Screening activities may be collected over more than one visit during the 7-day screening window if necessary; if screening and dosing occur at the same visit, only one evaluation is required, unless otherwise specified. The sample taken closest to dosing and prior to dosing is considered the baseline sample.

^b Assigned by the IRT system. See Section [6.3](#) for further information.

^c Collection of urine samples for urinalysis from participants who are unable to provide urine samples is not mandatory provided that a reasonable attempt has been made to collect the samples.

^d If urine tests positive or is indeterminate, a quantitative serum β -hCG will be performed for confirmation before the participant is enrolled in the study. Pregnancy testing is for baseline purposes only, and a participant with a positive urine pregnancy test can still participate in the study.

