5.1 Inclusion Criteria

Participants are eligible to be included in the study only if all the following criteria apply:

Age and Weight

- 1 Participant must be aged \geq 29 weeks GA to $<$ 18 years of age at the time of signing the informed consent (see Appendix A 3 for procedures around informed consent).
- 2 Participant must weigh a minimum of 1.5 kg.

Type of Participant and Disease Characteristics

COHORT 1: Participants who do not have COVID-19 and have not knowingly been exposed to a SARS-CoV-2 positive individual (pre-exposure prophylaxis):

- 3 At increased risk of severe COVID-19 for any of the following reasons:
 - (a) Immunocompromised state
 - (b) One or more comorbid conditions that increase the risk of severe COVID-19, eg, cardiovascular disease, including heart disease since birth, malignancy, chronic kidney disease, and genetic, neurologic, or metabolic conditions.
- 4 Medically stable defined as disease not requiring significant change in therapy or hospitalization for worsening disease during the one month prior to enrollment, with no acute change in condition at the time of study enrollment as judged by the Investigator.
- 5 Documented negative SARS-CoV-2 RT-PCR test collected \leq 3 days prior to Day 1 or a negative rapid SARS-CoV-2 antigen test at screening.
- 6 Prior to enrollment, participants must not have had COVID-19 symptoms (Table 13) within 10 days of dosing.

7 Increased risk for SARS-CoV-2 infection, defined as those whose locations or circumstances put them at appreciable risk of exposure to SARS-CoV-2 and COVID-19, based on available risk assessment at time of enrollment.

COHORT 2: Participants with COVID-19 and mild to moderate symptoms (treatment):

8 At increased risk of severe COVID-19 for any of the following reasons:

- (a) Immunocompromised state
- (b) One or more comorbid conditions that increase the risk of severe COVID-19 (see list in 3[b])

9 Medically stable defined as disease not requiring significant change in therapy or hospitalization for worsening disease during the one month prior to enrollment, with no acute change in condition at the time of study enrollment as judged by the Investigator.

10 Documented positive SARS-CoV-2 RT-PCR test collected \leq 3 days prior to Day 1 or a positive rapid SARS-CoV-2 antigen test at screening.

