6.1 Study Interventions Administered

6.1.1 Investigational Product

All eligible participants will receive a single dose of AZD7442 on Day 1, either IM (AZD8895 followed by AZD1061 administered separately) or a single IV infusion (AZD8895 and AZD1061 co-administered), and participants will be monitored for 365 days after IMP administration (Table 7). Dose levels will be stratified by body weight range categories. Age-appropriate quantities of all excipients are used within the AZD7442 formulation. All excipients are of pharmaceutical grade and are not considered to pose any safety issues for children at the anticipated exposure levels.

Table 7 Investigational Product: AZD7442

Intervention name	AZD7442 (AZD8895 + AZD1061) (AstraZeneca)
Type	Biologic
Dose formulation	AZD7442 is comprised of 2 drug products supplied as separate vials of AZD8895 and AZD1061. Each vial contains a solution of 100 mg/mL active ingredient (AZD8895 or AZD1061), 20 mM histidine/histidine-HCl, 240 mM sucrose, 0.04% (w/v) PS80, pH 6.0. The label claim volume for each vial is 1.5 mL and each vial contains 150 mg (nominal) of active ingredient.
Unit dose strength(s)	100 mg/mL of AZD8895 in a single vial 100 mg/mL of AZD1061 in a single vial
Dosage level(s)	The dose levels are stratified by body weight range categories as shown in Table 6 (prophylaxis of COVID-19/treatment of mild to moderate COVID-19: 60 to 600 mg IM or 50 to 440 mg IV; treatment of severe COVID-19: 60 to 600 mg IV).
Route of administration	IM (AZD8895 followed by AZD1061) or a single IV infusion (AZD8895 and AZD1061 concurrently)
Use	Experimental
Sourcing	AstraZeneca
Packaging and labeling	AZD7442 will be provided in glass vials. Each glass vial will be labeled as required per country requirement.

COVID-19, coronavirus 2019; IM, intramuscular; IV, intravenous, w/v, weight per volume.

Details of the batch numbers will be included in the Trial Master File, and the final CSR. Labels will be prepared in accordance with GMP and local regulatory guidelines. The labels will fulfill GMP Annex 13 requirements for labeling.

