8.2.1 Physical Examinations

A complete physical examination will be performed at screening followed by targeted physical examinations as specified in the SoA (Section 1.3).

- A complete physical examination will include, but not be limited to, assessment of height, weight, general appearance, head, ears, eyes, nose, throat, neck, skin, as well as cardiovascular, respiratory, abdominal, and nervous systems. Each clinically significant abnormal finding at screening will be recorded in the medical history.
- A targeted physical examination will include areas suggested by the medical history. Each clinically significant abnormal finding following IMP dosing will be recorded as an AE (Section 8.2).

All physical examinations will be performed by a licensed healthcare provider (eg, physician, physician assistant, or licensed nurse practitioner).

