8.2.2 Vital Signs

Vital signs, including heart rate, respiratory rate, pulse oximetry, BP, and body temperature, will be performed as specified in the SoA (Section 1.3). The participant should be resting prior to the collection of vital signs.

Situations in which vital sign results should be reported as AEs are described in Section 8.3.7.

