#### 4.2.1.7.4 Structural Population PK Model and Covariate Model Development

Based on prior experience, a 2-compartment model with fixed standard allometric exponents (0.75 for clearances and 1 for volumes) will be evaluated with the inclusion of an age-based maturation function for clearance to represent the paediatric population.

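### The SAP plans body weight matched to each PK sample time, but the protocol schedules weighing only at screening and no rule says where later weights come from

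*SAP*

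**What the plan says.** **What the model needs.** SAP 4.2.1.7.3 states that covariates that change over time will be considered so as to obtain "values that match the observation time of the dependent variable, such as age and body weight especially in the paediatric patients". SAP 4.2.1.7.4 makes weight a structural term, using "fixed standard allometric exponents (0.75 for clearances and 1 for volumes") and an age-based maturation function on clearance. The final model is to report bodyweight-adjusted clearance for each weight category (SAP 4.2.1.8).

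**What the schedule collects.** Protocol Table 1 lists "Complete physical examination, including height and weight" in the screening window, Day -7 to Day 1. Protocol 8.2.1 adds: "A complete physical examination will be performed at screening followed by targeted physical examinations as specified in the SoA". The later examinations are narrower: "A targeted physical examination will include areas suggested by the medical history". Protocol 8.2.2 does not include weight: "Vital signs, including heart rate, respiratory rate, pulse oximetry, BP, and body temperature, will be performed as specified in the SoA". Tables 2 and 3 have no weight row at any later visit or at early discontinuation.

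**When PK is sampled.** Protocol 4.2.1 and 8.5.2 set one sample between Days 4 and 15, then samples at Days 31, 92, 183 and 366, plus an end-of-infusion sample for IV participants.

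**The concern.** The analysis plan calls for an input that the schedule does not collect. Age at each sample follows from dates; weight does not. With no stated source, the analyst must either carry screening weight forward or choose a method after seeing the data.

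The choice matters most in the youngest children. Entry is allowed from 1.5 kg ("Participant must weigh a minimum of 1.5 kg"), and an infant's weight may double or more during the year of sampling. Because the exponents are fixed, growth that is not recorded has to go somewhere else: the clearance and volume estimates, the maturation function or the individual random effects. Model-derived concentrations and AUC are part of the primary PK endpoint (Protocol Section 3), and the study is meant to support the choice of paediatric dose (Protocol 4.2).

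Height has the same gap. Any later update of the height-based renal function estimate for children under 12 (SAP 4.2.1.7.3, derived covariates) would have no scheduled height to use.

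**Working it through.** The plan states no figure for this point, so there is none to reproduce. The check has two parts.

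**1. Is a later weight scheduled anywhere?**
- Table 1, screening: yes, in the complete examination.
- Tables 2 and 3, Visits 1 to 6 and early discontinuation: targeted examination and vital signs only, neither of which names weight.
- SAP 4.1.5: weight is summarised as a baseline characteristic only.
- SAP 4.2.1.7: no growth curve, interpolation or carry-forward rule.

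So no weight is scheduled after Day 1.

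**2. How large is the bias if screening weight is carried forward?**

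Inputs from the documents:
- Exponents 0.75 (clearance) and 1 (volume).
- Half-life of 366/4 = 91.5 days, because Protocol 4.2.1 equates 366 days with about 4 half-lives.
- IV sampling times: end of infusion and about 7, 30, 91, 182 and 365 days after dosing.
- The 70 kg reference weight given as an example in SAP 4.2.1.7.4.

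Assumptions, not in the documents:
- The growth figures in the table below.
- Decelerating growth with a time constant of 150 days.
- One compartment, no noise and no maturation term.

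Formulas, with r the ratio of final to screening weight and w(t) the weight at time t relative to screening:
- w(t) = 1 + (r - 1)(1 - exp(-t/150)) / (1 - exp(-365/150))
- k(t) = k0 × w(t)^(0.75 - 1), with k0 = ln 2 / half-life
- True concentration: C(t) is proportional to exp(-∫k dt) / w(t)
- Fit with weight held at screening: ln C = -ln V - (CL/V) × t, by least squares at the sampling times

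Two half-lives were used. One is 91.5 days at every size. The other treats 91.5 days as the 70 kg value and scales it by (weight/70)^0.25, which those exponents imply. For 3.5 kg that is 91.5 × (3.5/70)^0.25 = 43.3 days.

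Fitted value divided by the true value at screening weight:

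| Assumed growth over the year | r | CL, V at 91.5 d | Scaled half-life | CL, V at scaled half-life |
|---|---|---|---|---|
| 3.5 to 9.5 kg | 2.71 | 1.44, 1.22 | 43.3 d | 1.25, 1.26 |
| 8 to 11 kg | 1.38 | 1.12, 1.05 | 53.2 d | 1.07, 1.06 |
| 15 to 17 kg | 1.13 | 1.04, 1.02 | 62.3 d | 1.03, 1.02 |
| 30 to 33 kg | 1.10 | 1.03, 1.01 | 74.0 d | 1.03, 1.02 |

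The growth shape matters too. For r = 2.5 and a half-life of 91.25 days, fitted clearance is 1.39 times with decelerating growth and 1.29 times with linear growth. At 60 days the figures are 1.28 and 1.19.

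**The case against.** **The SAP does not promise a measured weight at every sample.** It says that time-changing covariates will be considered and that covariates are taken where they are available. Sites may weigh children anyway, and a clinic record or growth projection would satisfy the present wording. This stands: the covariate cannot be built from scheduled data, but it is not impossible to build. The statement that missing data will not be imputed (SAP 4.2.1.7.1) sits next to the rules for concentrations below the quantification limit, so its reach to covariates is unclear.

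**A reader might infer that infant clearance and volume will be estimated against the wrong weight.** The documents do not support that. Neither says that screening weight will be carried forward, and the SAP's stated intent is the opposite. The bias above is conditional on that rule.

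**A reader might take the scaling error at the last sample as the bias.** For 3.5 to 9.5 kg, weight at Day 366 implies clearance 2.71^0.75 = 2.11 times and volume 2.71 times the screening-weight values. At a 91.5-day half-life the true AUC is 0.64 of the constant-weight prediction. These are forward predictions. Fitted parameters move less, because the early samples are scaled to nearly the right weight.

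**A reader might extend the point to eligibility and dosing, because "Dose levels will be stratified by body weight range categories".** Both rest on a weight taken within 7 days of a single dose, so screening weight suits both. Observed concentrations and the non-compartmental parameters (SAP 4.2.1.1 to 4.2.1.3) use no later weight.

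**Pooling limits the effect on typical values.** The model includes several thousand adults (SAP Table 5), and the mismatch in a few infants could go to their random effects. The SAP does not say whether the maturation function is estimated or fixed, so absorption of growth by that function is possible but not shown.

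**Conclusion.** The point holds in a limited form. The SAP plans a time-matched weight that the protocol does not collect after screening, and no substitute is specified. Only the population PK results are exposed, mainly for infants.

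If screening weight were carried forward, fitted clearance would be about 1.25 to 1.44 times and volume about 1.2 to 1.3 times the screening-weight value for growth from 3.5 to 9.5 kg. Clearance would be about 1.07 to 1.12 times for 8 to 11 kg, and about 3% too high for 30 to 33 kg.

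These sizes rest on assumed growth, a simplified IV model without maturation or IM absorption, and individual fits rather than the pooled model. Steadier growth gives smaller figures. The number of children affected is unknown: the planned minimum under 1 year was 18 of 100 (Protocol Table 5), but enrolment stopped at 46 (SAP Section 2) and the documents give no age breakdown.

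The missing schedule item is certain. The size of the bias is illustrative.

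**What to change.** **For visits still outstanding:** add weight and height to the existing physical examination at Visits 3 to 6 and early discontinuation in Protocol Tables 2 and 3, and use that weight as the time-varying covariate. Enrolment has ended, so this helps only the remaining visits; the documents do not say how many there are.

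**For completed visits:** pre-specify in SAP 4.2.1.7.3 that weight comes from the clinic record nearest the sample. Failing that, project screening weight along an age- and sex-specific growth standard. Flag projected values in the dataset.

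**Sensitivity run:** refit with screening weight only for children under 15 kg, and report the change in clearance and volume for the two lowest weight categories.

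**Cost:** one weighing at visits that already include an examination, retrieval of clinic weights, and one derivation rule. The drawback is that some weights will be projected, and projection is less accurate for preterm or chronically ill children, both of whom the study admits.
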